## 3.1.2 Dose Escalation

All subjects, independently of the randomization arm, will start pomalidomide at 0.5 mg/d. Those randomized to the high-dose arm will escalate to the target dose level by increasing the pomalidomide dose in 0.5 mg increments (**Table 3**) every 2 weeks to the next level. If the escalation is not tolerated, the patient will be treated on the next lower dose level. MTD designation will be given to the highest dose in which no more than 1 DLT occurred per cohort.

Dose Level	Dose
Starting Dose (level 1)	0.5 mg daily on Days 1-14
Dose Level 2	1.0 mg daily on Days 15-28
Dose Level 3	1.5 mg daily on Days 29-42
Dose Level 4	2.0 mg daily on Days 43-56

Table 3. Pomalidomide Dose Escalation Steps (high-dose arm)

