## **Study Schema**

#### 3.1.1 Dose-Limiting Toxicity

DLT will be defined as any grade  $\geq 3$  adverse event which is thought to be probably or definitively related to the investigational drug administration (notable exceptions where grades 2 or lower can be considered as DLTs are indicated in Table 4 below in Section 3.3). In addition, any persons who are unable to tolerate the dose to which they are assigned will be counted as a DLT at the maximum dose explored for that patient. The time frame for evaluation in which toxicity will count towards a DLT will be up to 28 days after therapy received at a given dose

level. In addition, a grade  $\geq$  3 AE will not be considered as DLT if the adverse event is attributed to a GVHD flare and responds to steroid pulse therapy as outlined in section 4.1. Whether treated on either arm, if there are 2 patients in the first 6 who experience a DLT from a given dose level, then no further patients will be treated at that dose level on the trial, regardless of arm. Furthermore, when more than 6 patients have received a given dose level, if at any time 33% or more patients experience a DLT when treated at that dose level, then no further patients will be treated at that dose level, then no further patients will be treated at that dose level, then no further patients will be treated at that dose level, then no further patients will be treated at that dose level, then no further patients will be treated at that dose level, then no further patients will be treated at that dose level. Data from all subjects who receive  $\geq$ 1 dose of pomalidomide will be include in the safety analysis.

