## **3.3 DOSE MODIFICATIONS**

Patients requiring dose reduction will be reassigned to one of the lower dose cohorts being evaluated: 0.5, 1.0 or 1.5 mg. Patients may be dose reduced to the lowest possible dose, i.e. 0.5 mg. For any dose reductions or if study drug needs to be held greater than 35 days, the Principal Investigator (PI) or Lead Associate Investigator (LAI) must be contacted. Once a dose has been reduced, it cannot be re-escalated. At the discretion of the PI, the use of granulocyte colony-stimulating factor (G-CSF) will be permitted to manage neutropenic fever or a Grade 4 neutropenia. Given the potentially long treatments delays, patients must have received 75% of the doses prescribed to be considered evaluable for the primary study endpoint.

Common Terminology Criteria (CTCAE) Version 4.0	Adverse Event	Dose Change for Pomalidomide
Allergy/ Immunology	Allergic reaction/ hypersensitivity (including drug fever) - Grade 2	Hold study drug until resolved to < Grade 1; Decrease dose by 1 dose level
Allergy/Immunology	Allergic reaction/ hypersensitivity (including drug fever) - Grade 3 or 4	Discontinue Study Drug
Blood/Bone Marrow	Neutropenia (ANC) - Grade 3 with fever or Grade 4	Hold study drug until < Grade 2; Decrease dose by 1 dose level
Blood/Bone Marrow	Thrombocytopenia - Grade 3 or 4	Hold study drug until <grade 2;
Decrease dose by 1 dose level</grade>
Blood/Bone Marrow	Anemia - Grade 3 or 4	Hold study drug and treat anemia as needed until Hgb within 0.5 g/dL of lower limit of normal; Decrease dose by 1 dose level

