As an early stopping rule for futility, if after 7 patients have enrolled on either arm, 0 have responded, then no further patients will be accrued to that arm as soon as this can be determined. In practice, this means that patients may continue to be accrued beyond 7 in an arm, but no more patients would be registered and treated on that arm once the first 7 were evaluated and no PRs or CRs were identified in those first 7.

To protect patient safety, an early stopping rule will be implemented as follows. For patients treated on either arm, if 2 patients in the first 6, or 33% of the patients at any time experience a DLT at a given dose level, no further patients will be treated at that given level on the trial. Furthermore, when more than 6 patients have received a given dose level, if at any time 33% or more patients experience a DLT when treated at that dose level, then no further patients will be treated at that dose level. Thus, as an example, should there be 2 patients with a DLT in the first 6 who are able to receive 2.0 mg/day on the dose escalating arm, then subsequent patients treated on that arm will not be escalated beyond 1.5 mg/day.

With two arms, each of which has a maximal accrual of 16 patients, up to 32 evaluable patients will be randomized. In order to allow for a very small number of patients who are not able to be evaluated at all for response, the accrual ceiling will be set at 35.

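### Section 10 words the DLT closing rule more strictly than section 3.1.1, so the two sections disagree after one DLT in the first three patients; the MTD sentence in 3.1.2 also leaves its denominator undefined

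*Combined protocol and SAP*

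**What the plan says.** **Closing rule, section 3.1.1.** A level is closed, regardless of arm, "if there are 2 patients in the first 6 who experience a DLT from a given dose level". Once more than 6 patients have received the level, it is closed "if at any time 33% or more patients experience a DLT when treated at that dose level". The percentage test therefore has a minimum number of patients.

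**Closing rule, section 10.** The first safety sentence closes a level "if 2 patients in the first 6, or 33% of the patients at any time experience a DLT at a given dose level". This percentage clause has no minimum. The next sentence then gives the 3.1.1 version: "Furthermore, when more than 6 patients have received a given dose level, if at any time 33% or more patients experience a DLT". The worked example that follows uses 2 DLTs in the first 6 patients at 2.0 mg.

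**Who is exposed, section 3.1.2.** "All subjects, independently of the randomization arm, will start pomalidomide at 0.5 mg/d".

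**What counts, section 3.1.1.** Besides graded events, "any persons who are unable to tolerate the dose to which they are assigned will be counted as a DLT".

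**MTD label, section 3.1.2.** "MTD designation will be given to the highest dose in which no more than 1 DLT occurred per cohort". No cohort size is attached. Elsewhere the word has different meanings. The cohort table in section 2.5 lists one cohort, the whole study population. Section 3.3 uses it for dose levels: "Patients requiring dose reduction will be reassigned to one of the lower dose cohorts being evaluated".

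**The concern.** A safety stopping rule should give one answer for any sequence of outcomes. Here one DLT in the first one, two or three patients at a level closes it under the literal first sentence of section 10 and leaves it open under 3.1.1. The level where this matters most is 0.5 mg. Every new patient on either arm has to pass through it, so closing it ends treatment of new patients in the whole trial. A single DLT is also easier to reach than the graded definition suggests, because intolerance of the assigned dose counts as one.

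The MTD sentence raises a separate and smaller question. A fixed limit of one DLT suits a small cohort. Within the 32 evaluable patients, up to 16 may reach each escalated level and up to 32 take 0.5 mg. If all patients at a level form the cohort, the limit tightens as experience grows, and a dose that the closing rule keeps open may be ruled out as the MTD.

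**Working it through.** **Inputs.** The rules are as set out above; 16 patients per arm and 32 evaluable come from section 10. The documents give no true DLT rate p for these doses in this population, so p = 2%, 5% and 10% are assumptions. DLTs are taken as independent; write q = 1 − p.

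**The plan's own figures.** It states no operating characteristics for the DLT or MTD rules. Its efficacy design does reproduce: with 16 patients and success at 3 or more responses, exact binomial power at 30% is 0.9006 (stated 90%) and the type I error at 5% is 0.043 (limit 0.10). Nothing below touches those figures.

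**Closing rule: where the wordings part.** One DLT gives 1/1 = 100%, 1/2 = 50%, 1/3 = 33.3% and 1/4 = 25%. On the literal section 10 wording a level passes patient 3 only with no DLT. Under 3.1.1 it passes with 0 or 1.

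- Closed by patient 3, literal: 1 − q³
- Closed by patient 3, 3.1.1: 3p²q + p³
- Closed by patient 6, literal: 1 − q³(q³ + 3pq²), that is, no DLT in patients 1–3 and at most one in patients 4–6
- Closed by patient 6, 3.1.1: 1 − q⁶ − 6pq⁵

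For p = 10%, by patient 3: 1 − 0.729 = 0.271 against 0.027 + 0.001 = 0.028. By patient 6: 1 − 0.729 × 0.972 = 0.291 against 1 − 0.5314 − 0.3543 = 0.114.

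| Assumed DLT rate | By patient 3: literal section 10 | By patient 3: 3.1.1 | By patient 6: literal section 10 | By patient 6: 3.1.1 |
|---|---|---|---|---|
| 2% | 5.9% | 0.1% | 6.0% | 0.6% |
| 5% | 14.3% | 0.7% | 14.9% | 3.3% |
| 10% | 27.1% | 2.8% | 29.1% | 11.4% |

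**Which wording was meant.** Two DLTs within 6 patients is at least 2/6 = 33.3%. If the 33% test ran from the first patient, no sequence could meet the 2-in-6 clause without already meeting 33%, so that clause would do nothing. The sentence about more than 6 patients would also add nothing.

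**MTD label, if a cohort is everyone at the level.** Up to 6 patients the two rules agree: 1/6 passes both and 2/6 fails both. From patient 7 they part. For example, 2/7 (28.6%), 2/10 (20%) and 2/16 (12.5%) can all be open under 3.1.1 yet exceed one DLT. The chance of being open with 2 or more DLTs at 16 patients is P(open) − (q¹⁶ + 16pq¹⁵), with P(open) from an exact patient-by-patient recursion:

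- p = 5%: 0.9651 − 0.8108 = 0.154
- p = 10%: 0.8709 − 0.5147 = 0.356

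Sixteen is the maximum for an escalated level within the 32 evaluable patients. With 10 patients the figures are 5.2% and 13.9%.

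**MTD label, trial level.** What matters is the highest qualifying dose, so I simulated the whole trial: 40,000 runs, 16 per arm in random order, each patient finishing before the next, no escalation after a DLT, and no minimum number of patients for a level to be named. The reported MTD falls below the highest open level, or none is named although a level is open, in about 11%, 18% and 13% of trials at equal rates of 5%, 10% and 20% at every level. With rates rising 1/2/5/10% and 2/5/10/15% from 0.5 to 2.0 mg, the figures are about 32% and 39%.

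**MTD label, if a cohort is 6 patients.** One DLT at most per 6 is the 2-in-6 rule again, and among open levels there is no conflict.

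**The case against.** On the closing rule, the best defence is that section 10 corrects itself. The redundancy shown above, the sentence that follows, the worked example and section 3.1.1 all point to one rule. A reader might infer that the trial is meant to close a level after a single early DLT; the documents do not support that. What remains is that the clause is in the statistical section as written, and a team applying it literally would act differently from one applying 3.1.1.

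The assumed rates can also be challenged. Section 1.3.3.2 reports that grade 3 or 4 thrombocytopenia or neutropenia was rare in 58 myelofibrosis patients given 0.5 mg, and Table 2 records no adverse event as a reason for stopping in that study. The population differs, but this favours the 2% row over the 10% row at 0.5 mg. The literal wording still closes the level by patient 3 about 6% of the time at 2%.

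On the MTD sentence, a reader might infer that the count bars well-tolerated doses. That holds only if a cohort is everyone at the level. Section 3.3 favours that meaning, but section 1.3.3.1, describing an earlier myeloma study, ties a DLT limit to cohorts of up to 6, a convention the sentence may be following. A reader might also infer that a wrong label would distort the trial. It would not: the MTD is not a stated objective and enters neither the stopping rules, the arm selection nor the response endpoint, and the escalating arm works to each patient's own tolerated dose.

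**Conclusion.** The closing rule is wrong as written in section 10 and should be corrected. The two sections give opposite instructions after one DLT in the first three patients at a level. The probability of closure by then differs by about 6, 14 and 24 percentage points at assumed DLT rates of 2%, 5% and 10% (5.9 − 0.1, 14.3 − 0.7, 27.1 − 2.8). These figures rest on independent DLTs and assumed rates; the contradiction rests on neither. Section 3.1.1 is almost certainly the intended rule.

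The MTD sentence is a low-severity ambiguity. With everyone at the level as the cohort, an escalated level with 16 patients is open but barred 15% or 36% of the time at rates of 5% or 10%; with cohorts of 6 there is no conflict. Only the reported label is at stake.

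**What to change.** 1. **Section 10.** Delete the clause in the first safety sentence that applies the 33% limit at any time, leaving 2 DLTs in the first 6 there and the 33% test for more than 6 patients in the sentence after it. Section 10 then matches 3.1.1. Cost: one phrase and no new data. The downside is that a single early DLT no longer closes a level. If that extra caution is wanted, it should be stated openly in both sections.

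2. **Section 3.1.2.** Define the MTD as the highest level, arms pooled, that is not closed under 3.1.1 and has at most 1 DLT per 6 patients treated. Report DLTs over patients treated at every level beside it. On this ratio 2/16 (12.5%) qualifies, 3/16 (18.8%) does not, and a level with fewer than 6 patients qualifies only with no DLT. Cost: one sentence. It is looser than a fixed count of one for larger groups, but tighter than naming any level still open, which would admit 5/16 (31%).

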# 3.2 DRUG ADMINISTRATION

Pomalidomide will be given as 0.5 mg, 1.0 mg, or 2.0 mg capsules to be taken orally once a day on days 1-28 of a 28-day cycle. Each daily dose of pomalidomide should be taken at approximately the same time of day. Patients will be asked to complete a medication diary (Appendix P).

Pomalidomide capsules should be swallowed whole, and should not be broken, chewed or opened.

If a dose of pomalidomide is missed, it should be taken as soon as possible on the same day. If it is missed for the entire day, it should not be made up.

Patients who take more than the prescribed dose of pomalidomide should be instructed to seek emergency medical care if needed and contact study staff immediately.

Patients are instructed to fast (water or clear fluids only) for at least 2 hours prior to taking a dose to at least 1 hour post dosing. Pomalidomide should not be swallowed concurrently with other allowed medications while on-study.

# 3.2.1 Drug Dispensing

Pomalidomide (POMALYST®) will be provided to research subjects for the duration of their participation in this trial at no charge to them or their insurance providers. Pomalidomide will be provided in accordance with the Celgene Corporation's POMALYST REMSTM program. Per the standard POMALYST REMSTM program requirements, all physicians who prescribe pomalidomide for research subjects enrolled into this trial, and all research subjects enrolled into

this trial, must be registered in and must comply with all requirements of the POMALYST REMSTM program.

Drug will be shipped on a per patient basis by the contract pharmacy to the NIH pharmacy for IND studies. Only enough pomalidomide for one cycle of therapy will be supplied to the patient each cycle. This is in accordance with the POMALYST REMSTM program.

# Only enough pomalidomide capsules for 1 cycle of therapy may be provided to the patient each cycle.

Patients will be asked to maintain a dairy and bring to the next appointment all remaining capsules.

## **3.3 DOSE MODIFICATIONS**

Patients requiring dose reduction will be reassigned to one of the lower dose cohorts being evaluated: 0.5, 1.0 or 1.5 mg. Patients may be dose reduced to the lowest possible dose, i.e. 0.5 mg. For any dose reductions or if study drug needs to be held greater than 35 days, the Principal Investigator (PI) or Lead Associate Investigator (LAI) must be contacted. Once a dose has been reduced, it cannot be re-escalated. At the discretion of the PI, the use of granulocyte colony-stimulating factor (G-CSF) will be permitted to manage neutropenic fever or a Grade 4 neutropenia. Given the potentially long treatments delays, patients must have received 75% of the doses prescribed to be considered evaluable for the primary study endpoint.

Common Terminology Criteria (CTCAE) Version 4.0	Adverse Event	Dose Change for Pomalidomide
Allergy/ Immunology	Allergic reaction/ hypersensitivity (including drug fever) - Grade 2	Hold study drug until resolved to < Grade 1; Decrease dose by 1 dose level
Allergy/Immunology	Allergic reaction/ hypersensitivity (including drug fever) - Grade 3 or 4	Discontinue Study Drug
Blood/Bone Marrow	Neutropenia (ANC) - Grade 3 with fever or Grade 4	Hold study drug until < Grade 2; Decrease dose by 1 dose level
Blood/Bone Marrow	Thrombocytopenia - Grade 3 or 4	Hold study drug until <grade 2;
Decrease dose by 1 dose level</grade>
Blood/Bone Marrow	Anemia - Grade 3 or 4	Hold study drug and treat anemia as needed until Hgb within 0.5 g/dL of lower limit of normal; Decrease dose by 1 dose level

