#### 1.3.3.1 Pomalidomide in cGvHD

Pusic et al. reported results of a phase 2 study of pomalidomide in patients with cGvHD not controlled by corticosteroids. Eight subjects received 3 mg/day with dose reductions to 2 mg, 1 mg and 0.5 mg. Seven subjects required dose reduction because of muscle cramps, tremor and fatigue. Five subjects discontinued therapy for worsening of cGvHD of the skin and mouth (N=1), pain (N=1) and no response (N=3). No bone marrow suppression, somnolence, constipation or DVT were observed. Three persons reached the primary evaluation endpoint at 6 months at the 2 mg dose (N=2) or 1 mg dose (N=1). The 3 patients had global PRs per NIH criteria (skin erythema, GI) and <PR ongoing improvements in the skin, mouth and eyes. This study established feasibility of giving pomalidomide to humans with cGvHD and the absence of serious side effects at doses less than 2 mg/day.

Table 2.	Clinical	Studies	of Pon	nalidomide
----------	----------	---------	--------	------------

Reference	Setting	Study Design	Study Duration	Dose	N	MTD	Toxicities	Response Rate
Phase 1								
Celgene, not published	Healthy volunteers	Single-blind, placebo- controlled, ascending single dose		1, 5, 10, 25, 50 mg	30, 10 received placebo	N/A	Mild or moderate AEs; no clinically significant changes in any laboratory parameter tested	N/A
Streetly et al.,2008 	Relapsed MM	Standard dose escalation	4 weeks	1, 2, 5, 10 mg	20	5 mg	10 mg, grade 4 neutropenia in 3/3 pts, DVT 0%	10% CR and >50% reduction in paraprotein in 50%
Schey et al., 2004 	Relapsed or refractory MM	Dose escalating regimen	4 weeks	1, 2, 5, 10 mg	24	2 mg	Grade 3/4 neutropenia in 58% pts and DVT in 16%	17% CR, >25% reduction in paraprotein in 67%, >50% reduction in paraprotein in 54%
Phase 2								· • •
Tefferi et al. 2009 	Anemia associated with myelofibrosis	Randomized, double- blind, multicenter	Up to 12 28-day treatment cycles	4 arms (2 mg+ placebo, 2 mg + prednisone, 0.5 mg + prednisone, and prednisone + placebo	84	2 mg	Relatively low incidence of grade ≥3 neutropenia and thrombo-cytopenia	Response in anemia 20 pts (40%) 23%, 2 mg/d + placebo; 16%, 2 mg/d + prednisone; 36%, 0.5 mg/d + prednisone; 19%, prednisone + placebo

		D1 1/0	0.0.1		10			
Mesa et	Myelofibrosis	Phase $1/2$ ,	28 days	2.5, 3.0 and	19	3 mg	DLT myelosuppre-	7 pts anemia
al., 2009 68		multicenter		3.5  mg/day;			ssion in $2/3$ pts in	response, 2 spleen

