## **3 STUDY IMPLEMENTATION**

#### 3.1 STUDY DESIGN

The study is a randomized phase 2 trial with the single stage selection design. It is known from prior trials that the maximum tolerated dose of pomalidomide is about 3 mg/d in persons with bone marrow disorders receiving prior therapies for cancer, in cGvHD doses <3mg/d have been well tolerated. This study will explore clinical toxicity of gradual escalation of pomalidomide doses <3 mg/d in subjects with cGvHD. Patients will receive either a constant low dose of pomalidomide (0.5 mg/day) for six months or a strategy of increasing dose of pomalidomide from 0.5 mg/d up through each individual patients' maximum tolerated dose, with escalations by 0.5 mg/d every 2 weeks to a maximum of 2.0 mg/d. In each of the two arms, the trial will use a single stage design.

As an early stopping rule for futility as outlined in section **8**, if after 7 patients have enrolled on either arm, 0 have responded, then no further patients will be accrued to that arm as soon as this can be determined. To protect patient safety, an early stopping rule will be implemented. With two arms, each of which has a maximal accrual of 16 patients, up to 32 evaluable patients will be randomized. Safety assessments and pregnancy testing for FCBP will be performed at scheduled intervals as described in the Study Calendar.

Response will be assessed every 3 months while taking pomalidomide following the criteria in Section 6.2. The primary efficacy endpoint will be evaluated at 6 months. Efficacy outcome is defined as clinical response (CR or PR) in subjects who enter the study with stable cGvHD or stable disease for  $\geq$ 3 mo for subjects with progressive cGvHD at study-entry. (Stability will be assessed by the clinician and by the clinical exam at the screening evaluation based on the clinician estimate of the disease trajectory during the 3 months pre-randomization). Subjects who meet the response criteria at 6 months will continue therapy for another 6 months. If in the subject's best interest, efforts will be made to provide access to study drug on compassionate basis beyond the 12-month study endpoint.

Patients who discontinue therapy for any reason will be followed for up to 24 months after starting pomalidomide as described in Section **6.1.3**.

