3.6.1 Criteria for removal from protocol therapy

- Completion of 6- or 12-month course of protocol therapy (depending on the level of response)
- Progressive cGvHD or malignancy requiring new line of systemic therapy
- Participant requests to be withdrawn from active therapy
- Unacceptable toxicity as defined in Section **3.3**
- Dose interruption longer than 35 days
- Positive pregnancy test
- Investigator discretion

The PI is to be notified of all discontinuations from study drug. The reason for dose modification/discontinuation should be recorded in the CRF and in the patient's medical records.

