## 6.2 **RESPONSE CRITERIA**

### 6.2.1 Definitions

Evaluable for efficacy: Patients who complete 6 months of therapy will be evaluable for the secondary endpoint of efficacy assessment. Patients who progress earlier will be also included in the analysis of efficacy.

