#### 6.2.2.1 Response Criteria

Efficacy will be assessed using NIH consensus criteria measuring for therapeutic response in clinical trials for cGvHD:

- **CR** is defined as complete resolution in all of signs and symptoms at all affected organs or tissues.
- **PR** is defined as improvement in ≥ 1 organ or tissue with no progression in any other affected organ or tissue. The calculations for PR and progressive disease (PD) are provided in Appendix H and Appendix I.
- **Response** < **PR** is defined as change towards improvement from the pre-treatment baseline but not meeting the criteria for CR or PR.
- **Stable Disease** is defined as no change in cGvHD, SD will be considered as response in patients with documented cGvHD progression over preceding 3 months.
- **Flare** is defined as exacerbation of cGvHD manifestations during withdrawal of immunosuppressive therapy which do not exceed those at the beginning of the trial and improves after reinstatement of previous treatment.
- **Progressive disease** is defined as failure of therapy to control cGvHD. The calculations for progressive disease (PD) are provided in Appendix I. Assessment by Organ-Specific Criteria. Patients who progress prior to 6 months evaluation will be also evaluable for the primary efficacy endpoint.
- **Mixed response** (improvement in some organs but worsening in others) will be categorized as progressive disease.

As outlined in Section **3.5**, type of involved organ, location and its measurements will be recorded at scheduled evaluations and reported on the appropriate CRF, equal to "Chronic GVHD Assessment (Clinician) Form," (Appendix G). All other measurements not being included in primary assessment but clinically related to cGvHD (e.g., change of pigmentation) will be reported in the source documents.

Skin and skin appendages: Skin assessments include 4 anatomic level of skin involvement:

- (1) erythematous rash (epidermal),
- (2) movable sclerosis (dermal),
- (3) non-moveable sclerosis, hidebound skin, or involvement of subcutaneous tissue and fascia (subcutaneous) and
- (4) ulceration (full thickness loss of epidermal tissue).

The first 3 measurements should be taken separately and recorded in metric notation using a body surface area (BSA). A cutaneous assessment worksheet for recording the BSA is provided (Appendix J). The size of ulcer should be measured the longest diameter (LD) of the largest ulcer.

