# **10 STATISTICAL CONSIDERATIONS**

It is known from prior trials that the pomalidomide MTD is about 3 mg/d in persons with bone marrow disorders receiving therapies for cancer. Due to high frequency of pomalidomide dose de-escalation observed in preliminary cGvHD experiences when given at 3 mg/d, this study will explore clinical toxicity of gradual escalation doses below 3.0 mg.

The primary objective of this study is to determine if patients with cGVHD will experience an acceptable level of clinical response when treated with either a constant low dose of pomalidomide (0.5 mg/day) for six months or a strategy of increasing dose of pomalidomide from 0.5 mg/d up through each individual patients' maximum tolerated dose, with escalations by

0.5 mg/d every 2 weeks to a maximum of 2.0 mg/d. The study will thus randomize patients between fixed low dose and escalating dose to tolerance, and will be considered a randomized phase II trial with a selection design component.

In each of the two arms, the trial will be conducted using a single stage design. With 16 patients on each arm, an exact binomial test would have 90% power to detect a difference between a 5% response rate and a 30% response rate using a 0.10 one-sided significance level and an exact binomial test. In addition, after the trial has ended, the 80% and 95% confidence limits will be determined for each arm about the observed response proportion in order to aid in interpretation of the results. If there are 3 or more responses in 16 patients, this would be sufficient to rule out a 5% response rate and demonstrate consistency with 30% or better response rates.

At the conclusion of the study, if both arms are able to accrue to the full 16 patients, the arm with the greater number of responses will be selected for further investigation subsequently. That is, if the fixed, low-dose arm, or the increasing dose level arm, has the greater number of responses, then that arm would be studied further. In the event of a tie, the lower dose arm would likely be preferred. As an example, if the true probabilities of response on the two arms were 0.10 and 0.30, then the probability of correctly selecting the superior arm would be 93%, and if the true probabilities on the two arms were 0.15 and 0.30, the probability of correct selection would be 84%.

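### Sections 3.3, 6.2.1 and 6.2.2.1 do not give one evaluability rule for the primary 6-month response, and no section scores patients who stop early without progression

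*Combined protocol and SAP*

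**What the plan says.** Four places in the protocol bear on who counts for the primary response.

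- **Section 3.3:** "Given the potentially long treatments delays, patients must have received 75% of the doses prescribed to be considered evaluable for the primary study endpoint". It does not say whether the base is the full planned course or doses due to date, or whether held days count.
- **Section 6.2.1:** "Patients who complete 6 months of therapy will be evaluable for the secondary endpoint of efficacy assessment". The next sentence adds patients who progress earlier. There is no dose condition. The word secondary sits badly with Sections 3.1, 6.2.2 and 6.2.2.1, which treat 6-month response as the primary efficacy endpoint.
- **Section 6.2.2.1:** "Patients who progress prior to 6 months evaluation will be also evaluable for the primary efficacy endpoint". Again there is no dose condition.
- **Section 10:** the test and the interval estimates are set for 16 patients per arm ("the 80% and 95% confidence limits will be determined for each arm about the observed response proportion"). No analysis set is named beyond evaluable patients. The accrual ceiling is 35 against 32 planned, with this reason: "In order to allow for a very small number of patients who are not able to be evaluated at all for response".

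The endpoint itself is in Section 3.1: "Efficacy outcome is defined as clinical response (CR or PR) in subjects who enter the study with stable cGvHD or stable disease" lasting at least 3 months for those progressive at entry. For safety, Section 3.1.1 uses everyone who received at least one dose. Efficacy has no matching definition.

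Several routes off treatment involve no progression: the mandatory stops in Table 4 and, in Section 3.6.1, the patient's request, investigator discretion and "Dose interruption longer than 35 days". Section 6.1.3 describes follow-up after stopping. None of these places assigns a response category.

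**The concern.** The primary result is a proportion from about 16 patients per arm, so each patient moved in or out of the denominator is visible in the estimate. The sections select that denominator by different criteria: doses taken, time on therapy, or progression. If Section 3.3 or 6.2.1 is applied as written, the set is filtered after randomisation by who stays on treatment. Patients who stop for toxicity, pain or lack of benefit, most of whom are unlikely to be responders, would drop out of the rate. Because the rule is not fixed in the text, the choice also stays open until the data are in.

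The protocol's own cGvHD experience does not show that early stopping is rare. In the earlier 8-patient study described in Section 1.3.3.1, "Five subjects discontinued therapy for worsening of cGvHD of the skin and mouth (N=1), pain (N=1) and no response (N=3"). That study started at 3 mg/day, above this trial's 2.0 mg maximum. It shows that the question can arise and does not forecast the rate here.

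**Working it through.** **1. The plan's own figures.** Inputs from Section 10: n = 16 per arm, null 5%, target 30%, one-sided 0.10, success at 3 or more responses. Exact binomial: P(X ≥ 3 | 16, 0.05) = 0.043 and P(X ≥ 3 | 16, 0.30) = 0.901. The stated 90% power reproduces. A cut-off of 2 would give 0.189, so 3 is the smallest cut-off that keeps alpha below 0.10.

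**2. Does one patient get two answers?** Section 3.2 sets daily dosing in 28-day cycles. The Section 3.5 calendar puts the 3-month visit at cycle 4 day 1 and the 6-month visit at cycle 7 day 1.
- Planned doses: 6 × 28 = 168. The 75% cut: 0.75 × 168 = 126. Doses due by month 3: 3 × 28 = 84.
- *Completer with two 22-day holds.* Each hold is within the 35-day limit. (168 − 44)/168 = 124/168 = 74%. In under Section 6.2.1; out under Section 3.3 if held days count.
- *Progressor at month 3.* At most 84/168 = 50% of the planned course. In under Sections 6.2.1 and 6.2.2.1; out under Section 3.3 if the base is the full course.

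**3. Patients who stop without progression.** Section 6.2.1 lists completers and progressors only, so by implication these patients leave the denominator. Section 3.3 may also exclude them, depending on the base. No section calls them non-responders, carries an earlier assessment forward, or states that they are excluded.

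**4. Size of the effect on the estimate.** Suppose 3 responders among 16 treated, with three non-responding stoppers dropped (exact limits):

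| | Rate | 80% CI | 95% CI | One-sided p against 5% |
|---|---|---|---|---|
| 3/16 | 18.8% | 7.1-37.1% | 4.0-45.6% | 0.043 |
| 3/13 | 23.1% | 8.8-44.4% | 5.0-53.8% | 0.025 |

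In expectation, if a share d is excluded and those patients respond at rate q, a true 30% reads as (0.30 − d·q)/(1 − d). The ceiling leaves 35 − 32 = 3 extra places. If all three fall in one arm (an assumption), d = 3/19 = 15.8%:
- q = 0: 0.30/0.842 = 35.6%.
- q = 0.15 (an assumption): (0.30 − 0.0237)/0.842 = 32.8%.

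So a true 30% reads as 33-36%. Excluding responders at a rate above 30% would act the other way.

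**5. Effect on the test.** With 3 responders the test is positive on either denominator. With 2 responders: 2/16 gives p = 0.189, 2/11 gives 0.102 and 2/10 gives 0.086. Six of 16 would have to be dropped to change the result.

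**The case against.** The strongest reply is that the three sections can be read as one rule. Section 3.3 states a necessary condition. It does not say that everyone above 75% is in. The word also in Sections 6.2.1 and 6.2.2.1 can be read as adding progressors to a base group. The combined rule would be completers with at least 75% of doses, plus early progressors. Analysing evaluable patients, with a few extra places, is a recognisable phase 2 choice.

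Much of this stands, and it rules out some stronger readings:

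- *That the sections conflict however they are read.* They do not. A patient who stops for toxicity after enough doses passes Section 3.3 and is not listed in Section 6.2.1, but that is no contradiction, because passing a necessary condition does not admit anyone.
- *That the go/no-go decision is unsafe.* Step 5 of the working shows that it is hard to move.
- *That the escalating arm would lose more patients.* The documents do not show which arm would.
- *That the earlier study shows a doubling of the rate.* Applying the Section 6.2.1 list turns 3/8 = 37.5% into 3/4 = 75%, but only if the three stops for no response are not progression. Section 6.2.2.1 describes progression as failure to control the disease; if those stops count, the figure is 3/7 = 43%.

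What does not stand is that nothing needs changing. The combined rule is an inference that no section states. It leaves the base of the 75% undefined, and it still conditions the primary rate on remaining on treatment.

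**Conclusion.** The concern holds as a fault in the definition of the analysis set. The primary response has no single evaluability rule, two kinds of patient are classified differently depending on the section and on an undefined base, and patients who stop without progression have no stated outcome. The design arithmetic is sound.

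The harm is to the reported rate and its limits, which would be conditional on staying on treatment and probably too high. It is a few percentage points: 18.8% to 23.1% in the worked example, or 30% read as 33-36% if all three extra places fall in one arm. This rests on assumed exclusion fractions and on excluded patients responding less often than the rest; the documents give neither figure for this trial. It should be fixed, but it does not threaten the test.

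**What to change.** Amend Sections 3.3, 6.2.1, 6.2.2.1 and 10 together.

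1. **Primary set:** all randomised patients who took at least one dose. For the test and the confidence limits, count anyone without a documented 6-month response, as defined in Section 3.1, as a non-responder.
2. **Accrual:** no treated patient is then replaced, so state that accrual stops at 16 treated per arm and that the ceiling of 35 covers only patients never dosed. The 3-of-16 cut-off and the count-based selection rule then stand.
3. **If an arm exceeds 16 treated:** compare response proportions for selection. With equal true rates of 30% and 16 against 19 patients, the larger arm has more responses 56% of the time and the smaller 30%; with 16 in each it is 42% each way.
4. **Futility look:** use the first 7 treated and keep Section 10's wording, which counts PRs and CRs only.
5. **Sensitivity analyses:** keep the 75%-of-doses set and the completer-plus-progressor set. State the base of the 75% and how held days count.
6. **Label:** change secondary to primary in Section 6.2.1.

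**Cost:** no extra patients or visits, and a less favourable reported rate. If the 30% target was meant for evaluable patients only, the rate in the new set is 0.30 × (1 − d). At an assumed d of 10%, P(X ≥ 3 | 16, 0.27) = 0.848; at 30%, P(X ≥ 3 | 16, 0.21) = 0.684. Power then falls from 90% to about 85% or 68%.
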